[name]
[name]

GLOSSERY OF TERMS

ACASI	audio computer assisted self-interview
AIDS	acquired immunodeficiency syndrome
APP	mobile smartphone application
ART	antiretroviral therapy
CAB	community advisory board
CAI	condomless anal intercourse
CBT	cognitive behavioral therapy
CDC	Centers for Disease Control and Prevention
DBS	dried blood spot
DSM-5	Diagnostic and Statistical Manual of Mental Disorders-version 5
FCC	Friends Community Center
FRI	Friends Research Institute, Inc.
GPS	global positioning system
HIPAA	Health Insurance Portability and Accountability Act
HIV	human immunodeficiency virus
IRB	institutional review board
MA	methamphetamine
mHealth	mobile health
MSM	men who have sex with men
MTL	Molecular Testing Labs
NIH	National Institutes of Health
PEP	post-exposure prophylaxis
PrEP	pre-exposure prophylaxis
RA	research assistant
RCT	randomized controlled trial

SAE	serious adverse event
SOC	stages of change
STI	sexually transmitted infection

SCHEMA

***Getting Off:* A Theory-based mHealth Intervention for Methamphetamine-using MSM**

Lay Title: *Getting Off App*

DESIGN

Getting Off App is a randomized controlled trial (RCT) to assess the impact of *Getting Off*, a culturally competent Cognitive Behavioral Therapy-based app for reducing methamphetamine use, HIV sexual risk behaviors, and increase advancement along the HIV Prevention or Care Continuum, with the desired outcome of significant reductions in methamphetamine use and HIV sexual risk behaviors as well as increased odds of advancement along the HIV Prevention or Care Continuum among men who have sex with men (MSM), aged 18-65, who report using methamphetamine within the past year.

Over the course of 30-days, participants are asked to complete 24 intervention sessions in the *Getting Off* app derived from an existing, manualized, group-based intervention with established efficacy.

The study will implement a two-arm RCT to determine intervention effects through comparison of participants who are given immediate access to the *Getting Off* app (Immediate Delivery [ID]) and participants who are given access to the *Getting Off* app after a delayed 30-day period (Delayed Delivery [DD]).

DURATION

30 days

SAMPLE SIZE

300 participants (n=150: Immediate Delivery / n=150: Delayed Delivery)

POPULATION

MSM who are between the ages of 18 and 65 years of age, who have used methamphetamine within the past 365 days, who have their own Android or iOS running smartphone with a current data plan, and who are able and willing to provide informed consent and comply with study requirements.

1.0 STUDY OBJECTIVES

1.1 Specific Aims

- 1.1.1 Specific Aim 1a: Conduct a RCT to evaluate reductions of methamphetamine use and HIV sexual risk behaviors, and increased advancement along the HIV Prevention or Care Continuum using a two-arm RCT to determine intervention effects through comparison of the Immediate Delivery [ID] (n=150) and Delayed Delivery [DD] (n=150) arms.
- 1.1.2 Specific Aim 1b: Evaluate reductions in methamphetamine use and HIV sexual risk behaviors, and increased advancement along the HIV Prevention or Care Continuum using an observed treatment effects analysis powered for prospective sub-group analyses to compare longitudinal pre/post data from the pooled ID and DD arms (n=300);
- 1.1.3 Specific Aim 1c: Evaluate reductions in methamphetamine use and HIV sexual risk behaviors, and increased advancement along the HIV Prevention or Care Continuum using a two-arm historical matched comparison design to evaluate the outcomes of the *Getting Off* app (ID+DD; n=300) relative to a matched sample of participants having previously attended the brick-and-mortar group-based *Getting Off* intervention (n~600; total n=900).

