1.2 Secondary Aim

- 1.2.1 Secondary Aim 1: Determine the impact of structural- (e.g., housing insecurity, food scarcity, educational attainment, access to healthcare) and individual-level (e.g., homophobia, stigma, and discrimination) factors as moderators of intervention outcomes.

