6.6.2 Behavioral Assessments

6.6.2.1 DSM-5 Methamphetamine Use Disorder contains the DSM-5 diagnostic items necessary to make a determination of mild, moderate, or severe methamphetamine use disorder. This information will determine the app's utility for consumers at various levels of methamphetamine use. DSM-5 diagnostic criteria for other substance use disorders will also be collected. Administered at baseline only.

6.6.2.2 University of Rhode Island Change Assessment (URICA) is a brief, self-administered inventory used to assess the participant's current position regarding readiness for change (e.g., precontemplation, contemplation, action). Administered at all time points.

6.6.2.3 Admission/Follow-up Form collects demographic information, housing status, food security, educational attainment, alcohol and other drug use history, family and social history, legal status, HIV status, location on the HIV Prevention or Care Continuum, experiences with stigma and/or discrimination, and general and mental health status. The full form will be administered at baseline, an abbreviated version at all follow-up time points.

6.6.2.4 Substance Use Frequency is a brief assessment, developed by [name] (Principal Investigator) that assesses substance use, injection drug use, and injection protocols in the past 30 days. Administered at all time points.

6.6.2.5 Behavioral Questionnaire – Amphetamine (BQA)-Abbreviated Version gathers information on HIV-related drug and sexual risk behaviors, assesses self-efficacy for sexual behavior change, and collects detailed information on discrete sexual behaviors (with primary or non-primary partners and whether or not the behavior occurred under the influence of methamphetamine and/or other substances), as well as episodic data about participants' most recent sexual encounters. Administered at baseline, and an abbreviated version is administered at all follow-up time points.

6.6.2.6 PrEP Uptake and Adherence is a brief assessment, developed by [name] (Principal Investigator), that gathers information of PrEP readiness, initiation and adherence to access advancement along the HIV Prevention Continuum. Administered at all time points.

6.6.2.7 ART/HIV Care is a brief assessment, developed by [name] (Principal Investigator), that gathers information of HIV care and ART medication adherence to access advancement along the HIV Care Continuum. Administered at all time points.

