8.0 STATISTICAL ANALYSES

8.1 General Analytical Approach

All primary outcomes are operationalized and assessed in at least two discrete ways, increasing accuracy of measurements, reducing concerns of fully missing data, and allowing for post-hoc comparisons of concurrent validity across assessment modalities (see Table 2 for all outcome operationalizations). Descriptive statistics will be calculated and provided for all outcomes, with specific metrics chosen based on the distributional properties of each variable (e.g., counts and percentages for nominal variables; means and standard deviations for parametric continuous variables; ranges and medians for non-parametric continuous variables). Diagnostic (i.e., DSM-5), psychosocial (e.g., URICA), barriers and facilitators (e.g., housing insecurity, lack of transportation), and/or sociodemographic variables will be tested for significant association with study outcomes (i.e., advancement through the HIV Prevention or Care Continuum, methamphetamine use, HIV sexual risk behaviors), with specific tests of association chosen based on the distributional properties of the outcome variables in question. All variables demonstrating significant statistical association with one or more of the study outcomes will be included as statistical covariates in all multivariate outcome analyses associated with Specific Aims 1a-1c, and will additionally be included in exploratory sub-group analyses to test for moderating effects on treatment response and/or contingent effects among subsets of participants. Primary outcome analyses for Specific Aims 1a, 1b, and 1c will be carried out using mixed effects Generalized Linear Model (GLM) equations.

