9.2 Specific Aim 1b Analysis

Aim 1b completes the efficacy trial by doubling the size of the analytical sample and allowing for highly accurate specification of observed treatment effects; it is a single-arm, pooled (i.e., ID+DD) observed treatment effects analysis whereby data points from the ID arm are paired with their analytical comparators from the DD arm (i.e., ID enrollment data with DD 1-month post-enrollment data; ID 1-month post-enrollment data with DD 2-months post-enrollment data);

the proposed analytical model provides increased analytical power for HIV subgroup and/or contingency analyses, given the greater number of persons receiving the intervention relative to the proposed RCT model (i.e., N=300 receiving the app). Power Calculations for Specific Aim 1b: estimated pre-/post-test observed treatment effect MDEs for HIV Prevention or Care Continuum outcomes related to Specific Aim 3b are: 1) Di—OR = 1.61; 2) Cu—IRR= 1.35; for methamphetamine use outcomes: 1) Di—OR = 0.59; 2) Cu—IRR = 0.89; 3) Co—f2 = 0.01; for HIV sexual risk outcomes: 1) Di—OR = 0.63; 2) Cu—IRR = 0.85; 3) Co—f2 = 0.01.

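### Only the single-arm pooled pre/post model (Aim 1b) is described as powered for sub-group analyses; a sub-group difference in change there is not a difference in the app's effect, and moderator tests have no stated model

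*Combined protocol and SAP*

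**What the plan says.** Section 1.1.2 sets up Aim 1b as an "observed treatment effects analysis powered for prospective sub-group analyses to compare longitudinal pre/post data from the pooled ID and DD arms". The section headed 9.2 Specific Aim 1b Analysis says that "it is a single-arm, pooled (i.e., ID+DD) observed treatment effects analysis". It pairs "ID enrollment data with DD 1-month post-enrollment data", and ID month 1 with DD month 2. It justifies the pooling by power: "the proposed analytical model provides increased analytical power for HIV subgroup and/or contingency analyses".

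The other references to sub-groups and moderators name no model:

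- Section 8.1: variables associated with an outcome become covariates for Aims 1a to 1c and "will additionally be included in exploratory sub-group analyses to test for moderating effects on treatment response".
- Secondary Aim 1 (1.2.1): structural and individual "factors as moderators of intervention outcomes". Its examples are housing, food, education and access to care, and homophobia, stigma and discrimination.
- Section 6.6.2.1: DSM-5 severity, taken at baseline only, is to show the app's "utility for consumers at various levels of methamphetamine use".
- Table 2: DSM-5 and URICA are listed for exploratory sub-group analysis, and the admission form for HIV-related sub-group and moderator analyses. None is tied to the Aim 1b column.

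Section 9.1 reserves causal interpretation for the randomised comparison but describes no sub-group analysis within it.

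**The concern.** The pooled model has no concurrent untreated group, so the only sub-group test it offers is factor by time. That term contains any difference in the app's effect, but also the course each sub-group would have followed without the app. Where the sub-group is formed from baseline use, or from something measured with the same occasion error, it contains regression to the mean as well. Men enrolled in a heavy spell fall back and men enrolled in a light spell drift up, whatever the app does. Entry requires only some use in the past 365 days (5.1.2), so recent use can vary widely at enrolment.

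The DD waiting month is the trial's only untreated time. The Aim 1b pairing uses its end as DD's starting value and not as a control interval. At stake are statements about whom the app helps, together with an assurance of sub-group power that no calculation in the plan supports.

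**Working it through.** **Inputs.** From 8.2 and 8.3: 30% continuum advancement, 80% methamphetamine use, 65% sexual risk; two-sided 0.05, 80% power, two time points. From 9.1 and 9.2: 150 per arm for Aim 1a; N = 300 and odds ratios 1.61 / 0.59 / 0.63 for Aim 1b. The documents give no mean, SD or within-person correlation for days of use, so those are assumed below.

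**1. Reproducing the Aim 1b figures.** Power = Φ{(|p1−p2| − 1.96·√[2p̄(1−p̄)/n]) / √([p1(1−p1)+p2(1−p2)]/n)}. For use, odds are 4 × 0.59 = 2.36, so p2 = 0.7024. With n = 300 before and 300 after, treated as independent: (0.0976 − 1.96×0.0353)/0.0351 = 0.81, power 0.791. For continuum / use / sexual risk the powers are 0.793 / 0.791 / 0.791, and the solved detectable odds ratios are 1.617 / 0.587 / 0.627. The plan's figures reproduce, as whole-sample effects.

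**2. The same odds ratios in sub-groups.** The last row takes no effect in one half of the sample and the stated odds ratio in the other, with power = Φ(|ln OR|/SE − 1.96) and SE = √Σ1/[150·p(1−p)] over four cells. For use: 0.528/0.396 − 1.96 = −0.63, power 0.265.

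| Power at the stated Aim 1b OR | Continuum | Use | Sexual risk |
|---|---|---|---|
| Whole sample | 0.793 | 0.791 | 0.791 |
| Within half | 0.500 | 0.498 | 0.498 |
| Within a third | 0.359 | 0.357 | 0.357 |
| Sub-group-by-time ratio | 0.274 | 0.265 | 0.276 |

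The sub-group-by-time ratio of odds ratios detectable with 80% power is 2.66 / 0.335 / 0.386.

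**3. Regression to the mean with an inert app.** Split a normal variable at its enrolment median; the halves differ by 2√(2/π) = 1.596 SD. With month-to-month correlation r, the false difference in change in the ID arm (months 0 to 1) is −1.596(1−r) SD. In the DD arm (months 1 to 2) it is zero under exchangeable correlation and −1.596(r−r²) SD under AR(1). Averaging the two equal arms:

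- exchangeable: −0.798(1−r) SD
- AR(1): −0.798(1−r²) SD

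With an assumed SD of 8 days, the exchangeable formula gives −3.2 days at r = 0.5 and −1.9 at r = 0.7. AR(1) gives −5.8 at r = 0.3 and −1.2 at r = 0.9.

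**4. Simulated false-positive rates** (inert app, N = 300, Aim 1b pairing):

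- Median split on baseline days, latent mean 8 and SD 8 limited to 0-30 days, r from 0.3 to 0.9. Exchangeable: −4.1 to −0.6 days, significant in 99% to 39% of trials (r = 0.5: −3.0 days, 96%; r = 0.7: −1.9 days, 84%). AR(1): −5.2 to −1.2 days, 100% to 90%. These sizes agree with step 3, allowing for the limits at 0 and 30. Fixing half the variance as stable, a different assumption, gave 91-93% in one set of runs, inside that range.
- Severity score sharing part of the baseline error: 13-54% across the assumptions tried.
- Stable marker sharing no error: about 4-6%.
- Arm-by-factor interaction on the randomised month 0-1 change: about 4-6%.

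**5. Price of the randomised test.** For change scores the standard-error ratio is √(4/75)/√(2/150) = 2. With 75 per cell and no effect in one sub-group, power for a ratio of odds ratios equal to the Aim 1a detectable effect (1.97 / 0.48 / 0.52) is 0.278 / 0.261 / 0.276. For use: 0.734/0.556 − 1.96 = −0.64. The ratio detectable with 80% power is about 4.0 for continuum, 0.21 for use and 0.26 for sexual risk.

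**The case against.** A reader might infer that the plan assigns its moderator tests to Aim 1b. It does not: Secondary Aim 1, 8.1 and Table 2 name no model, so for moderators the fault is under-specification.

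A reader might also infer that Secondary Aim 1 will be distorted by regression to the mean. Its factors are structural and stigma-related, and the one sub-group named for Aim 1b is HIV. None of these is defined from baseline use. For HIV status or housing the risk is differing trends, of unknown direction and size.

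The plan defines no median split on days of use. Table 2 operationalises DSM-5 as presence of disorder or a count of criteria, which may be fairly stable. DD's later starting value removes about half the artefact under exchangeable correlation when the split is made at enrolment. HIV sub-group analyses may simply be separate estimates within strata, because the two continua have different steps. And the plan already keeps causal language for Aim 1a and calls the 8.1 sub-group tests exploratory.

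All of this stands, and it limits the claim. It does not supply a model in which a sub-group difference in effect can be estimated, and it does not support the claim of sub-group power.

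**Conclusion.** The point holds in two parts. First, the only model described as powered for sub-groups cannot separate a difference in the app's effect from a difference in course, and the moderator tests have no model at all. Second, the Aim 1b detectable effects are whole-sample figures, with power of about 50% within half the sample and about 27% for a sub-group-by-time ratio of the same size. Those two powers treat before and after values as independent, which is the calculation that reproduces the plan's own figures; positive within-person correlation would change them.

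The stronger statement, that an inert app will appear to work better in heavier users, is not supported. It can, if heaviness is defined by baseline use or by a measure sharing its error, possibly DSM-5 severity or URICA. The false-positive rate then ranges from roughly 39-100% for baseline days of use to about 13-54% for a partly contaminated severity score, and falls to about 5% for a stable marker. All of these rest on assumed distributions and correlations.

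**What to change.** - In 8.1 and 9.2 (Aim 1b), state that moderators and between-sub-group differences in effect are tested as arm-by-factor interactions on the randomised month-1 contrast of Aim 1a.
- Label Aim 1b sub-group pre/post changes, including estimates within HIV strata, as descriptive.
- In 1.1.2, remove the claim of power for sub-groups, or restate it with sub-group and interaction detectable effects.
- If pooled data are also modelled, include DD enrolment to month 1 as untreated time, enter month as a categorical term interacting with the factor, and read moderation only from factor-by-app. Linear time is not enough: with an inert app and a baseline-use split it left a bias of +0.8 to +2.9 days. Because only DD is assessed at month 2, identification then rests on the month 0-1 contrast, and the plan should say so.

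The cost is wording and model terms, with no new data. The downside to state is precision: about twice the standard error of the pooled contrast and 26-28% power for an interaction the size of the Aim 1a detectable effect, so moderator results will be exploratory. The remedy also reaches only outcomes measured at month 1. Section 6.6.3 places the HIV, STI, viral-load and PrEP biomarkers at baseline and months 3, 6 and 9, by which time both arms have been given the app.

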1.2 Secondary Aim

- 1.2.1 Secondary Aim 1: Determine the impact of structural- (e.g., housing insecurity, food scarcity, educational attainment, access to healthcare) and individual-level (e.g., homophobia, stigma, and discrimination) factors as moderators of intervention outcomes.

2.0 INTRODUCTION

2.1 Rationale

Methamphetamine use among MSM is associated with increased rates of HIV prevalence and transmission, as well as substandard advancement along the HIV Prevention and Care Continua. Methamphetamine use among MSM is deeply integrated into socio-sexual networks including the use of smartphone apps and websites to find sexual partners. Given the growth of mobile health technology, it is no longer necessary or reasonable to limit methamphetamine treatment options to physical sites, clustered in urban areas, and administered using generic, non-tailored content. The project builds upon the established efficacy of our manualized methamphetamine-use treatment intervention, “*Getting Off: A Behavioral Treatment Intervention for Gay and Bisexual Male Methamphetamine Users*,” and the highly promising findings from the successful Stage I proof-of-concept study, to complete translation of *Getting Off* into a cross-platform (iOS and Android) app and assess the app’s efficacy *and* non-inferiority in a scientifically rigorous randomized trial. The *Getting Off* app, like the group-based intervention before it, will use the principles of Cognitive Behavioral Theory and Stages of Change to help MSM reduce or eliminate methamphetamine use and HIV sexual risk behaviors, and increase advancement along the HIV Prevention or Care Continuum (including uptake of HIV testing, pre-, and post-exposure prophylaxis [PEP/PrEP] and PrEP adherence and persistence for those who are HIV negative; ART uptake and adherence for those who are HIV positive).

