6.0 PROJECT PROCEDURES

6.1 Recruitment

Four recruitment strategies are being utilized to ensure enrollment targets are met and a diversity of participants are enrolled. Furthermore, the diversity in recruitment strategies will foster a range in the sociodemographic profiles. All potential participants who inquire about the study are scheduled for an intake within 24-48 hours.

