6.1.4 Long-chain Referral Sampling

Current study participants will be asked to recruit potential new participants. Current participants will receive \$2 when they bring a potential participant to the site and \$18 if an eligible participant enrolls.

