6.4 Random Assignment

Following informed consent and completion of the baseline assessment, participants will be randomized to either the ID or DD arm through a computerized variable-balanced block randomization procedure. Recent work with MSM with substance use disorder (predominantly methamphetamine) at FCC revealed treatment outcomes to be associated with participant substance use histories and sociodemographics. A variable-balanced procedure will thus provide multivariate balance among the characteristics known or expected to influence outcomes. The randomization procedure will balance across age (<34, ≥ 34), race/ethnicity (Caucasian/White, all other race/ethnicities), HIV serostatus (+, -), and SOC (contemplation/preparation, action/maintenance).

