6.5 Incentive Schedule

Incentives are comprised of 1) incentives for baseline assessment (\$40 gift card); 2) incentives for completing follow-up assessments [\$50 gift card for completing the 1-month follow-up assessment, the 2-month follow-up assessment (DD arm only), the 3-month follow-up assessment, the 6-month follow-up assessment, and the 9-month follow-up assessment]; 3) incentives for self-administering and returning the at-home HIV/STI test kits within 45 days of receipt [\$50 gift card for returning after the 3-month assessment, after the 6-month assessment, and after the 9-month assessment] and 4) a \$2 gift card when an active participant brings a potential participant to the site to screen for eligibility, and an additional \$18 gift card if the potential participant is eligible and enrolls (maximum of three eligible and enrolled participants per active participant). Participants randomized into the ID arm can thus earn a maximum of \$450 in gift cards. Participants randomized into the DD arm can earn a maximum of \$500 in gift cards.

All participants may earn up to \$50 in gift cards each time they provide all requested biological marker samples or test results at the follow-ups, if conducted at-home and returned within 45 days of receiving the kit. HIV-positive participants may earn a \$20 gift card for returning a complete at-home test kit for Chlamydia, N. gonorrhoea and Syphilis. If the DBS sample is insufficient for processing the Syphilis test, participants will be asked to provide results of a recent (within 3 months) Syphilis test from their medical provider, or to come to the study site for an in-person blood draw. HIV-positive participants may earn the additional \$30 gift card (totaling \$50 in gift cards) for providing recent (within 3 months) HIV viral load test results from their medical provider, or by coming to the study site for a blood draw. HIV-negative participants may earn the full \$50 gift card for returning a complete at-home test kit for Chlamydia, N. gonorrhoea, Syphilis and HIV. Including, an additional DBS card for PrEP (TDF/FTC or TAF/FTC), if

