8.3 HIV Sexual Risk Behavior

HIV sexual risk behavior outcomes will be assessed at all time points throughout the study, and will be operationalized dichotomously (e.g., incident STI via biomarker testing), as a counted variable (e.g., number of days/times engaged in CAI in the past 30 days), and as a continuous variable (e.g., a HIV risk severity index generated from multiple factor-analyzed items). Power calculations for engagement in HIV sexual risk behaviors assume a 65% probability of engagement during the pre-intervention period for participants in the DD arm (equivalent to ~2:1 odds of engagement). Multivariable inferential analyses of dichotomous outcomes will take the form of GLMs employing the Bernoulli family and logit link function; counted outcomes will be analyzed with GLMs employing the Poisson-log or negative binomial link functions as distributional patterns dictate (note: if data evidence an over-representation of zeros or an overdispersion of variance, zero-inflated Poisson and/or negative binomial analyses may be substituted); continuous outcomes will be analyzed using GLMs employing the identity link and Gaussian family functions and assume a single covariate unless otherwise stated (note: iteratively reweighted, bootstrapped, or jack-knifed estimation procedures may be used in Gaussian models if sensitivity analyses indicate undue influence from outliers). Mixed effects GLM models are considered the best linear unbiased estimators for repeated measures data employing non-parametric and/or limited dependent variables. All power calculations are premised on tests of association across two time points (e.g., baseline with app completion; app completion with brick-and-mortar program completion), providing the most conservative estimate of minimum detectable effect (MDE) size estimations; all power calculations assume $\alpha \leq 0.05$ (two-tailed), and $1 - \beta = 0.80$.

Table 2: Instruments, Targets, Variable Operationalizations, and Minimum Detectable Effects

Table 2: Instruments, Targets, Variable Operationalizations, and Minimum Detectable Effects (1 - β = 0.80; α = 0.05, two-tailed)

Instrument	Target	Variable Operationalizations			Power-- Minimum Detectable Effects		
		Dichotomous (Di)	Count (Cu)	Continuous (Co)	Model 1— RCT (Aim 1a; n=150/n=150)	Model 2— Tx Effects (Aim 1b; N = 300)	Model 3— Matched Comparison (Aim 1c; N = 300/N ~ 600)

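### Paid chain referral links participants to one another, but the stated models and detectable effects name no dependence between men, so Aim 1b and 1c intervals may be too narrow

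*Combined protocol and SAP*

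**What the plan says.** Section 2.1 gives the background: "Methamphetamine use among MSM is deeply integrated into socio-sexual networks including the use of smartphone apps and websites to find sexual partners".

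Section 6.1 lists referral among its approaches: "Four recruitment strategies are being utilized to ensure enrollment targets are met and a diversity of participants are enrolled". Section 6.1.4, whose title describes long-chain referral, states: "Current study participants will be asked to recruit potential new participants". Section 6.5 sets the limit at a "maximum of three eligible and enrolled participants per active participant". A recruit who enrols becomes an active participant and may recruit in turn, so the limit applies to each man and not to the chain.

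Under Section 6.4, "participants will be randomized to either the ID or DD arm through a computerized variable-balanced block randomization procedure". The balancing factors are age, race/ethnicity, HIV serostatus and stage of change. Recruiter and referral chain are not among them.

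Section 8.1 says that the primary analyses for all three aims "will be carried out using mixed effects Generalized Linear Model (GLM) equations", without specifying the random effects. Section 8.3 supports that choice by calling these models the "best linear unbiased estimators for repeated measures data". Repeated measurement is the only dependence named. Sections 8 and 9 contain no chain term, cluster-robust variance, ICC or design effect.

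**The concern.** Men who recruit one another may share use occasions, venues and risk settings, so their outcomes, or their changes over the app period, may be positively correlated. What that does depends on the aim.

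- **Aims 1b and 1c.** Whole chains sit on one side of the comparison: all 300 app users supply the pre/post change, and all 300 form the app side against about 600 historical participants. Unmodelled positive correlation then understates the standard error. Aim 1c is meant to show non-inferiority, and there an interval that is too narrow makes a favourable conclusion easier to reach.
- **Aim 1a.** Men are randomised one by one, so chains are split across arms and the test keeps its size. The remaining question is whether a man in the immediate arm could influence a linked man in the delayed arm during the 30-day wait.

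**Working it through.** **Inputs from the documents.** 150 per arm (Aim 1a), 300 pooled (1b), 300 against about 600 (1c); two-sided 0.05 and power 0.80 (8.3); base rates 30% for continuum advancement, 80% for methamphetamine use and 65% for sexual risk (8.2, 8.3); detectable odds ratios from Table 2.

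**The limit of three.** The Section 6.5 maxima reproduce with it: 40 + 4×50 + 3×50 + 3×20 = $450 for the immediate arm, and one more $50 visit gives $500 for the delayed arm.

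**Do the stated detectable effects allow for links?** The base rate and odds ratio give the second proportion (30% with OR 1.61 gives 40.8%). I then used two-proportion power with pooled variance, no continuity correction and all observations independent.

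| Aim | Stated OR (continuum / use / risk) | Power under independence |
|---|---|---|
| 1a, 150 v 150 | 1.97 / 0.48 / 0.52 | 0.807 / 0.796 / 0.796 |
| 1b, 300 pre v 300 post | 1.61 / 0.59 / 0.63 | 0.793 / 0.791 / 0.791 |
| 1c, 300 v 600 | 1.52 / 0.62 / 0.66 | 0.806 / 0.828 / 0.821 |

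The Aim 1c row puts the base rate in the historical group; with it in the app group the powers are 0.799 / 0.817 / 0.817. The figures are close to 0.80 throughout, so they contain no allowance for linked men. Aim 1b reproduces only if pre and post values are treated as two independent samples.

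**Size if links matter.** Let f be the share of app users in linked clusters, m the cluster size and ICC the correlation of the analysed quantity. All three are assumptions.

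- Design effect on the app users: DE = 1 + f(m−1)ICC.
- Aim 1b: the variance ratio is DE, and the ICC is that of the within-person change.
- Aim 1c: only the 300 app users carry DE. With equal variances the ratio is (DE/300 + 1/600) / (1/300 + 1/600) = (2·DE + 1)/3.
- True type I error of an unadjusted 5% test: 2[1 − Φ(1.96/√ratio)].

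| Assumed case | DE | Effective N of 300 | Type I error, 1b | Ratio and type I error, 1c |
|---|---|---|---|---|
| f 0.25, m 2, ICC 0.02 | 1.005 | 299 | 5.1% | 1.003; 5.0% |
| f 0.5, m 4, ICC 0.10 | 1.15 | 261 | 6.8% | 1.10; 6.2% |
| f 1, m 4, ICC 0.20 | 1.60 | 188 | 12.1% | 1.40; 9.8% |

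For the middle case, DE = 1 + 0.5×3×0.10 = 1.15. The standard error grows by √1.15 = 1.07 in Aim 1b and √1.10 = 1.05 in Aim 1c. Once the links are allowed for, power at the stated continuum odds ratio falls from 0.79 to 0.74 (1b) and from 0.81 to 0.77 (1c). In the high case it falls to 0.59 and 0.67.

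With one unreferred man per cluster, these cases imply 300·f·(m−1)/m referred men: about 38, 113 and 225 of 300. The high case therefore makes referral the dominant source of enrolment.

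**Check by simulation.** With clusters of 4 across the whole sample, ICC 0.10 and 10,000 runs, an unadjusted test rejected in 4.8% of null trials for Aim 1a and 9.1% for a pooled test of change. The formula gives 8.6% for the latter (DE 1.30).

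**The case against.** The strongest reply is that none of the quantities that set the size is in the documents. Referral is one of four strategies, and if few men come that way the design effect is close to 1. Section 2.1 is general background and does not say that recruits are their recruiters' sexual partners; the referral payment is only for bringing someone to the site. This stands, and it is why the result is a range that starts at negligible.

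Other points also stand:

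- A reader might infer that the men will be analysed as independent. That is shown only for the power figures. The mixed models leave their random effects open, and a chain term is not excluded.
- In Aim 1b each man is his own comparator, so a shared baseline level largely cancels and the ICC of change may be small. Section 8.1 also adjusts for covariates associated with outcome, which could lower any remaining correlation.
- Because the Aim 1b figures ignore within-person correlation, a correlation of about 0.13 would offset a DE of 1.15 in power (1.15 × 0.87 ≈ 1.00). It would not repair the type I error.

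A reader might also infer that linked men in opposite arms dilute Aim 1a. A linked pair does fall in opposite arms with probability 150/299 ≈ 0.50, and the trial is not blinded. But Section 6.3 opens the app by randomised arm, and any spill-over would have to act before or within a 30-day wait. Moving the delayed arm 5% of the way towards the immediate arm would cut power to 0.75–0.76, and 10% would cut it to 0.70–0.72, but no source supports either percentage. Dilution is possible and cannot be sized.

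**Conclusion.** The concern holds in a limited form. The plan builds paid referral chains into recruitment, while its models and detectable effects name no dependence between participants. If linked men are positively correlated, Aim 1b and 1c intervals may be too narrow. Under the assumed cases the true error of a nominal 5% test runs from about 5% to about 12% in Aim 1b and about 10% in Aim 1c, with 6.8% and 6.2% in the middle case.

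The documents do not support saying that the intervals are too narrow, that the Aim 1a contrast is diluted, or that Aim 1a has an inflated type I error. This is a cheap improvement to the analysis plan. It does not invalidate the design, and it removes an uncertainty that could not be resolved later if the referral links were missing from the analysis file.

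**What to change.** 1. Carry the recruiter ID into the analysis file. The site must already know it to pay the referral incentive. Report the share of the 300 who were referred and the distribution of chain sizes.
2. In both sections numbered 9.2 (Aims 1b and 1c), specify standard errors clustered on referral chain, or a chain random effect. Men with no recorded link and all historical participants enter as singleton clusters.
3. Keep the intention-to-treat contrast as primary in Section 9.1. Do not exclude linked men from the delayed arm alone: that would unbalance the arms by recruitment channel, and some links form after randomisation. Any contamination check should be exploratory, should define linkage by whether the recruiter had app access when the recruit enrolled, and should apply equally to both arms.

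The cost is one linkage variable and some wording, with no extra participants or visits and no change to randomisation. The downside is slightly wider intervals for Aims 1b and 1c. If links turn out to be few, the results will barely move.
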